The Value of a High-Volume Image-Guided Injection in Chronic Midportion Achilles Tendinopathy: a Double-blind, Randomized, Placebo-controlled Clinical Trial

NCT02996409

13-8-2019

Statistical analysis plan HAT-study

The patients will be analyzed by intention-to-treat. To test for the effect of treatment on the between-group difference in primary outcome (VISA-A score), we will use the Generalized Estimation Equations (GEE) model. Adjustments will be made for the following baseline variables: age, sex, BMI and duration of symptoms. The same approach will be used for the following secondary outcomes: modified Öhberg score (0-4+ score), VAS score during 10-hop test, flexibility m. gastrocnemius, flexibility m. soleus, power m. gastrocnemius, power m. soleus.

Fisher's exact tests will be performed for the following secondary outcomes: Return to desired sport (categorized, we will dichotomize for: no return to sport and return to sport, not to desired sport combined as no return to sport; return to sport, not at pre-injury level and return to sport at pre-injury level combined as return to sport), patient satisfaction (categorized, we will dichotomize for: good/excellent as satisfied, moderate/poor as dissatisfied), and patient acceptable symptoms scale (PASS; categorized, symptoms acceptable/not acceptable).

Missing data will not be imputed, however sensitivity analyses will be performed if missing data is more than 5%. The researcher who will perform the analyses will be blinded to the allocated treatment. No interim analyses were planned for this study. Given the large amount of data derived from this trial, we intend to present the results in multiple papers.

Update 12-8-2019: We excluded the baseline VISA-A score as adjusted variable in the GEE-model, since adjustments are already being made as the baseline VISA-A score is included in the model as time point. Therefore, our biomedical statisticians stated that it was not necessary to adjust for this variable twice.

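### Baseline VISA-A is dropped as a covariate because it is a time point, but the SAP names no model term or contrast that would make this an adjustment

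*SAP*

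**What the plan says.** The first paragraph of the SAP gives the aim of the primary analysis as "To test for the effect of treatment on the between-group difference in primary outcome (VISA-A score") and the method as "we will use the Generalized Estimation Equations (GEE) model". The covariates follow: "Adjustments will be made for the following baseline variables: age, sex, BMI and duration of symptoms". Baseline VISA-A is not among them.

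The closing paragraph, headed Update 12-8-2019, explains why: "adjustments are already being made as the baseline VISA-A score is included in the model as time point", so that "it was not necessary to adjust for this variable twice". Baseline VISA-A is therefore one of the repeated outcome values.

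The first paragraph extends the method to six further outcomes: "The same approach will be used for the following secondary outcomes".

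The SAP does not say whether the model has a treatment-by-time term, whether the arms are held equal at baseline, which working correlation is used, or which coefficient, visit or contrast is the primary test.

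**The concern.** The update makes a statistical claim and removes a covariate from the primary model on the strength of it. The claim is true only under conditions that the SAP does not state. Once baseline is an outcome row, the effect of treatment is no longer a single obvious coefficient:

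- With treatment and time as main effects, it is the arm difference averaged over all visits. One of these is the pre-treatment visit, where randomisation makes the true difference zero.
- With an interaction and baseline as the reference visit, the row labelled treatment is the baseline difference. The effect sits in several visit-specific terms, none of them designated primary.

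At stake are a diluted estimate in the first case, and in the second an unassigned primary test that is less precise than it need be. Because this is a change that the SAP itself makes to the primary model, it is not a detail that can be assumed to lie in the protocol.

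**Working it through.** **Inputs.** From the SAP: baseline is an outcome row; baseline VISA-A is not a covariate; no contrast is named. The SAP gives no sample size, power, SD, effect size or number of visits, so there is no figure of its own to reproduce. Assumed: k = 2, 3 or 4 follow-up visits plus baseline; exchangeable within-patient correlation ρ = 0.3, 0.5 or 0.7; a constant effect δ after baseline; 1:1 allocation; complete data; two-sided 5% test. Variances are per arm with outcome variance 1; the common factor 2/n cancels in every comparison.

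**Power conversion.** 80% power corresponds to z = 1.96 + 0.84 = 2.80. If a test has a fraction r of the reference test's standardised effect, its power is Φ(2.80r − 1.96).

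**Reading 1: treatment plus time.**

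Expected coefficient = (0 + kδ)/(k+1) = δ·k/(k+1), that is 0.67δ, 0.75δ and 0.80δ for k = 2, 3 and 4. This holds for an independence or exchangeable working correlation. Under AR(1) with ρ from 0.3 to 0.7 it is 0.71δ to 0.62δ at k = 3.

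Variance of the all-visit mean: (1 + kρ)/(k+1). Variance of the follow-up mean without baseline adjustment: (1 + (k−1)ρ)/k. At k = 4, ρ = 0.5 these are 3/5 = 0.600 and 2.5/4 = 0.625, so r = 0.80 × √(0.625/0.600) = 0.816 and power = Φ(0.33) = 63%.

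Power of the treatment main effect where the unadjusted follow-up average has 80%:

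| k | ρ = 0.3 | ρ = 0.5 | ρ = 0.7 |
|---|---|---|---|
| 2 | 54% | 51% | 49% |
| 3 | 61% | 58% | 57% |
| 4 | 64% | 63% | 62% |

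This isolates the dilution, since neither test uses a baseline adjustment.

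**Reading 2: treatment-by-time interaction, baseline as reference.** At one follow-up visit the variance is:

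- baseline-constrained contrast, or equivalently baseline as covariate: 1 − ρ²
- change from baseline (the interaction term): 2(1 − ρ)
- plain visit difference (treatment row plus interaction term): 1

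Hence r = √((1−ρ²)/(2(1−ρ))) = √((1+ρ)/2) for the change contrast and r = √(1−ρ²) for the plain difference. At ρ = 0.3 the change contrast has r = √0.65 = 0.806 and power Φ(0.30) = 62%.

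Power where the baseline-constrained contrast has 80%:

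| Test | ρ = 0.3 | ρ = 0.5 | ρ = 0.7 |
|---|---|---|---|
| Change from baseline | 62% | 68% | 73% |
| Plain visit difference | 76% | 68% | 52% |

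**Simulation check.** 150 GEE fits of each model (assumed k = 3, 40 per arm, SD 20, ρ = 0.5, δ = 12). Treatment plus time gave a mean treatment coefficient of 9.18 (theory 0.75 × 12 = 9). With the interaction, the last-visit term averaged 12.40 and the treatment row −0.13.

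**Working correlation.** A baseline constraint gains precision only if the working correlation is not independence. With k = 1 and 40 per arm, its standard error in SD units is √(2/40) = 0.224 at every ρ under independence, but 0.213, 0.194 and 0.160 at ρ = 0.3, 0.5 and 0.7 under exchangeable.

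**The case against.** The strongest objection is that the SAP contains no model equation. It neither includes nor excludes an interaction, so a reader might infer that the primary estimate is shrunk towards zero, and the document does not support this. The update's own reasoning points the other way, if anything: calling the baseline row an adjustment makes sense when arms are compared relative to baseline, and makes none in a main-effects model. This stands, and the dilution is therefore stated as conditional. It does not remove the point, because a change contrast is less precise than a baseline-constrained one at every ρ below 1, and no contrast is designated.

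A reader might also infer that the all-visit main effect always has less power than a single-visit test. That is not so. Where a baseline-constrained single-visit test has 80% power, the main effect at k = 4 has 90%, 71% and 45% at ρ = 0.3, 0.5 and 0.7. For example, at ρ = 0.3, r = 0.80 × √(0.91/0.44) = 1.15. Averaging several visits can outweigh dilution when correlation is low, but the estimate is still biased towards zero.

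The interaction branch is partly a hazard of reading output: nothing in the SAP says that the baseline row would be reported as the effect. What remains is that the SAP does not say which row would be.

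Finally, the protocol may name a primary visit. That would settle the visit, but not the model terms or the update's claim. Nor does the SAP say that all six secondary outcomes have a baseline row, so the carry-over is limited to those that do.

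**Conclusion.** The point holds as a defect in how the SAP fixes its primary model. The reason given for dropping baseline VISA-A is valid only with a common baseline mean or a change-from-baseline contrast, and neither is stated.

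On the treatment-plus-time reading the estimate is 67% to 80% of a constant effect (k = 2 to 4). Against an unadjusted follow-up average with 80% power, power is 49% to 64% over the assumed range, and 62% to 64% at k = 4. On the interaction reading there is no dilution, but the change contrast at one visit has 62% to 73% power where a baseline-constrained contrast has 80%.

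All sizes rest on assumed k and ρ, exchangeable correlation, a constant effect and complete data. The documents do not show which model was intended, so they do not show that the trial's estimate is biased. The change should be made, because on either reading a better-defined model is available at almost no cost.

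**What to change.** In the first paragraph and the update, replace the description of the primary test with wording to this effect:

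*Visit is a categorical factor. Baseline VISA-A is an outcome row with a mean common to both arms, and treatment effects are fitted at post-baseline visits only, with a stated working correlation other than independence. [Alternatively: only post-baseline visits are modelled, with baseline VISA-A as a covariate.] The primary test is one named post-baseline contrast: the between-group difference at the protocol's primary visit, or the post-baseline average if that is the intended estimand. The treatment main effect over all time points is not used.*

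Delete the statement that a time point alone adjusts for baseline. Apply the same wording to those of the six secondary GEE outcomes that are measured at baseline.

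The cost is a sentence or two of SAP wording and no new data. The SAP does not say whether unblinding has taken place; if it has, the change should be dated and labelled accordingly. Choosing a single visit over an average settles the estimand and can cost precision when within-patient correlation is low, but the result is not diluted by the baseline visit.

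### If the treatment effect is the group-by-time contrast, the four listed covariates entered as main effects add essentially nothing, because baseline VISA-A is kept only as a time point

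*SAP*

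**What the plan says.** The first paragraph of the SAP sets the primary analysis of VISA-A: "we will use the Generalized Estimation Equations (GEE) model". It then states "Adjustments will be made for the following baseline variables: age, sex, BMI and duration of symptoms". All four are fixed at entry and do not vary over a patient's visits.

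The closing update of 12-8-2019 changes the role of the baseline score: "We excluded the baseline VISA-A score as adjusted variable in the GEE-model". The reason given is that adjustment for it is already achieved, since "the baseline VISA-A score is included in the model as time point". Baseline VISA-A is therefore a row of the outcome vector and not a covariate.

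The first paragraph carries the model over to six further measures: "The same approach will be used for the following secondary outcomes". They are the Öhberg score, pain on the hop test, and two flexibility and two power measures.

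The SAP does not name the treatment contrast. It also does not say whether the groups share one baseline mean, whether covariates interact with time, or which link, working correlation and type of standard error are used. On missing data it says "Missing data will not be imputed, however sensitivity analyses will be performed if missing data is more than 5" per cent.

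**The concern.** The update claims that a baseline row already adjusts for baseline. That makes sense only if the treatment effect is measured relative to baseline, that is, as the between-group difference in change, or group by time. In the ordinary form of that model a covariate entered as a main effect shifts all of a patient's rows, baseline included, by the same amount. It therefore disappears from the change. The result would be labelled as adjusted for four factors but would be the unadjusted comparison of change scores.

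Two things are at stake. One is the accuracy of the label on the primary result and on the secondary outcomes analysed in the same way. The other is efficiency: the trial collects prognostic variables and then uses them in a form that cannot sharpen the treatment comparison or correct for imbalance in factors that predict change.

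**Working it through.** The SAP gives no sample size, standard deviation or effect size, so there is no figure to reproduce. The cancellation is algebra and needs no such inputs. The sizes below come from simulation on assumed inputs.

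**1. Algebra.** Take an identity link, a free mean for each group *g* and time *t*, covariate main effects, and complete data. For any common working correlation the fitted cell parameter is

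α(g,t) = Ȳ(g,t) − X̄(g)·γ.

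The group-by-time contrast is

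[α(1,t) − α(1,0)] − [α(0,t) − α(0,0)] = [Ȳ(1,t) − Ȳ(1,0)] − [Ȳ(0,t) − Ȳ(0,0)].

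X̄(g)·γ enters each bracket once with each sign and drops out. A patient's residual change, r(i,t) − r(i,0), is also free of X, so the sandwich standard error is unchanged.

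**2. Numerical check.** Assumed: 80 patients, 1:1, baseline plus 3 follow-ups, residual SD 18, within-patient correlation 0.5 given the covariates, prognostic covariates, Gaussian GEE. In one complete data set the last-visit contrast was 2.72969 (robust SE 4.01855) both without and with the four covariates, under exchangeable, independence and unstructured working correlation. Over 60 replicates, under exchangeable and independence correlation, the shift was 0.0000 and the robust SE ratio 1.0000.

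**3. Where the cancellation weakens** (same assumed inputs):

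- Missing visits, exchangeable: SD of the shift 0.11 points at 5% missing and 0.21 at 15%; robust SE ratio 0.9996 and 0.998.
- Missing visits, independence: SD of the shift 0.45 and 0.89, largest 1.3 and 2.5 points; robust SE ratio 0.994 and 0.983.
- Model-based SE, complete data: 4.061 to 4.092 (exchangeable), 4.075 to 4.086 (unstructured), 6.129 to 5.781 (independence). The estimate does not move.
- One shared baseline mean, exchangeable: SD of the shift 0.85, largest 2.2 points; SE ratio 0.973.
- Group effect averaged over all rows, no interaction, one data set: 8.88 (SE 3.51) to 7.15 (SE 3.79). Here the covariates act. However, with *k* follow-ups and a constant effect δ after baseline, the average over *k* + 1 rows is δ·k/(k + 1). With *k* = 3 that is 0.75δ.
- Logit link (illustrative binary outcome, n = 2000): interaction 0.525 (SE 0.109) to 0.636 (SE 0.130), so no cancellation.

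**4. What the covariates could be worth.** A separate single simulated data set assumed 80 patients, 3 follow-ups, correlation 0.5, and follow-up depending on BMI and symptom duration. Its standard errors for the last-visit contrast were:

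- baseline row, with or without covariate main effects: 4.370
- baseline row plus covariate-by-time terms: 4.147
- post-baseline rows only, with baseline VISA-A and the four covariates: 3.542

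Variance ratios:

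- four covariates made effective: (4.370/4.147)² = 1.11
- then moving to the post-baseline model with baseline VISA-A as covariate: (4.147/3.542)² = 1.37
- both steps: (4.370/3.542)² = 1.52

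In the step 2 setting, with covariates made to predict change, covariate-by-time terms moved the estimate from 4.312 (SE 4.096) to 3.396 (SE 3.928): (4.096/3.928)² = 1.09.

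As a cross-check on the second step, the variance of a change score relative to a baseline-adjusted comparison is 2(1 − ρ)/(1 − ρ²) = 2/(1 + ρ). That is 1.54, 1.33 and 1.18 at ρ = 0.3, 0.5 and 0.7.

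**The case against.** The strongest reply is that the SAP never writes down the model in which the covariates vanish. Keeping baseline as a time point fits several models, and in some of them (a shared baseline mean, a time-averaged group effect) the covariates do change the answer. This stands, and it is why the point is conditional. A reader might infer that the SAP's adjustment is void whatever is fitted, or that no standard error can change. The document does not support that, because exact cancellation needs free baseline means, an identity link, complete data and a robust standard error, and the SAP states none of these. The reply does not remove the point. A shared baseline mean requires a constraint that the SAP does not mention, and a time-averaged effect adjusts for nothing at baseline and dilutes the effect.

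A second reply is that differencing already removes any covariate effect that is the same at baseline and follow-up. This also stands. Only imbalance in factors that predict change is left uncorrected, and under randomization the group-by-time contrast is not biased in expectation.

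Third, a reader might take 1.52 as the price of the ineffective covariates. It is not: most of it comes from bringing baseline VISA-A back as a covariate.

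Fourth, extension to every secondary outcome goes too far. The update speaks only of the VISA-A baseline, and the ordinal Öhberg score might be given a non-identity link, for which the cancellation need not hold.

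**Conclusion.** The point holds conditionally. Under the group-by-time reading with unconstrained baseline means and an identity link, the stated main-effect adjustment leaves the estimate and robust standard error exactly unchanged with complete data. With modest missingness under exchangeable correlation they are almost unchanged. That result rests on algebra, not on assumed inputs. Under independence working correlation with missing visits the estimate can move by a point or more, but the standard error gains little.

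The consequence is lost precision and lost protection against imbalance in predictors of change. The gain forgone on the four covariates is about 1.1 as a variance ratio (1.09 and 1.11 in two simulated settings). It depends on assumed prognostic strength, for which the SAP gives no evidence. The plan should be changed, but the issue does not invalidate the trial.

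**What to change.** Preferred: analyse post-baseline VISA-A values only, with treatment, time and treatment by time, and with baseline VISA-A, age, sex, BMI and symptom duration as covariates. Report the treatment contrast at the trial's primary follow-up visit. The four covariates and the baseline score then enter that contrast directly.

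Alternative, if the baseline row is kept: name group by time as the treatment contrast, state how the baseline means are handled, and add covariate-by-time terms (at least baseline versus follow-up) for the four variables. With free baseline means this makes the four covariates effective but does not recover the gain from baseline VISA-A as a covariate.

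Use the same form for the repeated secondary outcomes that have a baseline measurement and an identity link, and state the model for the Öhberg score separately.

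Cost: a line or two in the SAP and a changed model call; the variables are already listed there. The post-baseline model fits five covariate terms (baseline plus four), and patients with no follow-up value do not contribute to it. The alternative adds four terms if each covariate is crossed with baseline versus follow-up, and more if crossed with every visit.

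### Is it an error to analyse the five-grade modified Öhberg score with the same GEE as VISA-A?

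*SAP*

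**What the plan says.** The SAP is a single short text without numbered sections. Its first paragraph sets the primary analysis: "To test for the effect of treatment on the between-group difference in primary outcome (VISA-A score), we will use the Generalized Estimation Equations (GEE) model". Covariates follow: "Adjustments will be made for the following baseline variables: age, sex, BMI and duration of symptoms". The modified Öhberg score is then placed under that model ("The same approach will be used for the following secondary outcomes: modified Öhberg score (0-4+ score"), in one list with "VAS score during 10-hop test, flexibility m. gastrocnemius, flexibility m. soleus, power m. gastrocnemius, power m. soleus".

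The second paragraph sends three other outcomes to Fisher's exact test. Two are ordered scales collapsed to two levels, return to sport and satisfaction; for the latter: "patient satisfaction (categorized, we will dichotomize for: good/excellent as satisfied, moderate/poor as dissatisfied". The third, the acceptable-symptoms outcome, is binary already.

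The update of 12-8-2019 explains why baseline VISA-A is not also a covariate: "the baseline VISA-A score is included in the model as time point".

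No link function, outcome distribution, working correlation or effect measure is given for any of the GEE models.

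**The concern.** A label running from 0 to 4+ describes grades. If VISA-A is modelled through its mean, using the same approach for the grades gives a between-arm difference in mean grade. That scores the step from 0 to 1+ the same as the step from 3+ to 4+, and it fits means to a scale on which patients may gather at 0. Return to sport and satisfaction, which are also ordered, are handled as categories, so the plan can look inconsistent.

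If this were a real fault, the Öhberg result could depend on an arbitrary scoring, opposite movements at the two ends of the scale could cancel, and some power could be lost. The primary analysis would not be affected.

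**Working it through.** The SAP gives no sample size, effect size or grade distribution, so there is no figure of its own to reproduce. Every numerical input below is an assumption.

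**1. What is fixed.** GEE is a family of models that includes cumulative-logit versions for ordered outcomes. The SAP names the family only. The rest of this check takes the less favourable reading, a mean difference in grades.

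**2. Validity of the test.** If treatment does nothing, randomised arms share one grade distribution, so their mean grades agree whatever the spacing. Robust standard errors do not need normal data. Simulated settings: identity link, exchangeable correlation, robust standard errors, baseline as a time point, three visits, within-patient correlation 0.5, no covariates, 400 runs per cell.

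| Starting grades | 20 per arm | 40 per arm | 60 per arm | Average |
|---|---|---|---|---|
| Evenly spread | 6.75% | 5.25% | 6.75% | 6.25% |
| 50% at grade 0 | 6.0% | 7.0% | 5.0% | 6.0% |
| Mostly high | 5.75% | 5.5% | 4.25% | 5.2% |

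The standard error of each cell is √(0.05 × 0.95 / 400) = 1.1 points. Rejection is near 5%, at most slightly above, and the floor setting is no worse than the even one.

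**3. Meaning of the estimate.** With scores 0 to 4, the mean grade equals the sum over the four cut-points k of P(grade ≥ k). A difference in means is therefore the sum of four differences in proportions. Take two assumed distributions over grades 0 to 4, A = (0.30, 0.10, 0.10, 0.20, 0.30) and B = (0.10, 0.25, 0.35, 0.20, 0.10):

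| Cut-point | A | B | A − B | Odds ratio |
|---|---|---|---|---|
| ≥ 1 | 0.70 | 0.90 | −0.20 | (0.70/0.30)/(0.90/0.10) = 0.26 |
| ≥ 2 | 0.60 | 0.65 | −0.05 | (0.60/0.40)/(0.65/0.35) = 0.81 |
| ≥ 3 | 0.50 | 0.30 | +0.20 | (0.50/0.50)/(0.30/0.70) = 2.33 |
| ≥ 4 | 0.30 | 0.10 | +0.20 | (0.30/0.70)/(0.10/0.90) = 3.86 |

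The mean difference is −0.20 − 0.05 + 0.20 + 0.20 = +0.15 grades, a defined quantity.

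**4. Would an ordinal model remove the problem?** In this example the mean difference does depend on scoring: +0.15 with 0, 1, 2, 3, 4; +0.95 with 0, 1, 2, 4, 8; and −0.25 with 0, 2, 3, 3.5, 4. But the distributions were built to cross. The cut-point odds ratios run from 0.26 to 3.86, so proportional odds fails as well, and a fitted common odds ratio is about 1.26. Opposite shifts cancel there too.

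**5. Power.** Two-sample mean test against rank test, five levels, common odds ratio 3, 40 per arm. Grade 0 shares refer to the reference arm.

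| Share at grade 0 | Effect | Mean test | Rank test | Gap |
|---|---|---|---|---|
| 20% (even) | away from 0 | 0.774 | 0.779 | 0.5 points |
| 50% | away from 0 | 0.756 | 0.758 | 0.2 points |
| 70% | away from 0 | 0.667 | 0.712 | 4.5 points |
| 50% | towards 0 | 0.621 | 0.667 | 4.6 points |
| 70% | towards 0 | 0.421 | 0.482 | 6.1 points |

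With 3000 runs, the standard error of one estimate is about 0.8 points, so the first two gaps cannot be told from zero. These two-sample tests stand in for the two GEE models; neither GEE was compared directly.

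**6. Price of the alternative.** With grades at 70/15/8/5/2%, the top grade expects 0.02 × 40 = 0.8 patients in a 40-patient arm and is empty with probability 0.98^40 = 0.45, so its threshold would be poorly estimated. Using baseline grade as a covariate would also depart from the repeated-measures structure that the update describes for VISA-A.

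**The case for a change.** The strongest argument for the concern is textual. The SAP speaks of a between-group difference, and a cumulative-logit model would hardly count as the same approach as one for VISA-A. The mean difference in grades is indeed the plain reading, and the SAP gives no reason for grouping a graded score with measurements. That stands, but it shows only that the effect measure could be stated more fully.

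A second argument is that a mean difference mixes the treatment effect with the share of patients at 0. For a common odds ratio of 3, it is −0.84 grades when grades are even, −0.55 with 50% at 0 and −0.33 with 70% at 0. The arithmetic is sound, but the data were generated with a constant odds ratio, so only that measure could stay constant. Absolute effects normally vary with the starting distribution. The GEE simulation also shows power at 40 per arm falling from about 69% with high starting grades to about 15% with half at 0, but it has no ordinal comparator, so the fall cannot be blamed on the linear model.

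The charge of inconsistency is weak. Return to sport and satisfaction are collapsed to two levels and get no ordinal analysis either. Keeping all the Öhberg grades uses more information than that, and using different methods for different outcomes is no contradiction.

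**Conclusion.** The concern does not hold. On the plainest reading the plan gives a near-valid test and an estimate in grades. The possible loss is 0 to about 6 percentage points of power on one secondary outcome. The larger losses arise only with half or more of the reference arm at grade 0, which is an assumption without support in the SAP. The proportional-odds alternative exchanges equal spacing for another assumption, can hide opposite shifts in the same way, and strains with sparse top grades.

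These sizes rest on assumed arm sizes, grade distributions and effects, and the power figures on two-sample tests in place of the GEE models. The conclusion does not depend on their exact values: numeric scoring and proportional odds are both defensible for a five-grade secondary outcome. What remains is that the link and effect measure are not named, which is a missing detail and no error in the plan.

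### Low-priority improvement, not an error: Boschloo's exact test would keep the same 5% limit as the planned Fisher's test for return to sport, satisfaction and PASS, and never has less power

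*SAP*

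**What the plan says.** The SAP has no numbered sections. Its first paragraph analyses VISA-A with GEE and states: "Adjustments will be made for the following baseline variables: age, sex, BMI and duration of symptoms". It then adds "The same approach will be used for the following secondary outcomes" and lists six of them.

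The second paragraph treats three further secondary outcomes differently. Fisher's "exact tests will be performed for the following secondary outcomes": return to desired sport, patient satisfaction and PASS. The first two are collapsed to two categories, and PASS is already binary. No covariates are named for these three.

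The third paragraph says that missing data are not imputed. The SAP gives no significance level, sample size or allocation ratio.

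**The concern.** Fisher's test conditions on both margins of the two-by-two table. The conditional distribution is coarse, so in arms of moderate size the test cannot use its full 5% and its true error rate stays below it. Unused error rate is lost power: some real differences in return to sport, satisfaction or PASS are missed that an equally strict exact test would detect.

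These are also the only listed outcomes not analysed with the four covariates, which raises the question whether an adjusted analysis would serve them better. What is at stake is efficiency on three secondary outcomes. The validity of the trial's conclusions is not in question.

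**Working it through.** The SAP has no figure of its own to reproduce on this point.

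**Inputs**
- From the SAP: Fisher's exact test, two groups, three binary outcomes.
- Assumed: two-sided 5%; independent binomial outcomes; 30 to 50 analysed patients per arm; response rates from 5% to 95% in 5-point steps. With equal arms this gives 19 × 18 / 2 = 171 rate pairs.

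**Step 1: Boschloo's test cannot do worse.** Boschloo's test orders tables by their Fisher p-value and takes as its p-value the largest probability, over all common rates π, of a Fisher p-value as small as the one observed. Given any margin total, P(Fisher p ≤ c) ≤ c. Averaged over margins this still holds for every π. So the Boschloo p-value never exceeds the Fisher p-value, and every table that Fisher's test rejects is rejected too.

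**Step 2: size.** For rejection region R and arms n₁, n₂, the maximum size is max over π of Σ_R Bin(x; n₁, π) · Bin(y; n₂, π), over all tables (x, y) in R.

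| Arms | Fisher, maximum size | Boschloo, maximum size | Boschloo cut-off on the Fisher p-value |
|---|---|---|---|
| 30/30 | 2.74% | 4.69% | 0.0692 |
| 40/40 | 3.30% | 4.77% | 0.0707 |
| 50/50 | 3.52% | 4.87% | 0.0693 |

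Fisher's size does not rise steadily with arm size: it is 3.56% at 33/33 and 3.75% at 42/42. Over equal arms of 30 to 50 the range is therefore 2.7% to 3.8%. With equal arms the conditional distribution is symmetric and p-values tie in pairs; an imbalance of one patient breaks the ties. Fisher's size is then 3.97% at 30/31, 4.48% at 40/41, 4.39% at 49/50 and 4.75% at 41/42. The last is the largest of all 231 pairs of arm sizes from 30 to 50.

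**Step 3: power.** Power is Σ_R Bin(x; n₁, p₁) · Bin(y; n₂, p₂). Gain of Boschloo's test over Fisher's, in percentage points:

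| Arms | 50% vs 75% | 40% vs 70% | Median where Fisher's power is 40% to 80% |
|---|---|---|---|
| 30/30 | 8.9 | 8.6 | 6.8 (range 3.8 to 9.2) |
| 40/40 | 8.0 | 3.9 | 6.0 (2.6 to 8.0) |
| 50/50 | 6.3 | 2.6 | 5.1 (2.5 to 7.5) |
| 30/31 | 3.7 to 4.2 | 0.8 to 1.0 | 3.9 |
| 40/41 | 1.7 to 2.1 | 0.1 to 0.2 | 2.2 |
| 49/50 | 2.6 to 3.0 | 0.2 to 0.3 | 2.6 |

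For unequal arms, the ranges at the two named rate pairs cover both ways of assigning the rates to the arms. Other unequal pairs give medians of 2.6 (38/42), 2.9 (30/35) and 3.3 (45/47). Within the 40% to 80% band the largest single gain is 9.6 points (30/35), and the smallest is close to 0. Where Fisher's power is 90% or more, the gain with equal arms of 30, 40 and 50 is at most 2.7, 1.9 and 1.9 points, and usually near zero.

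**Step 4: one table.** For 15/30 vs 23/30, Fisher's p = 0.060 and Boschloo's p = 0.035. The risk difference is 0.767 − 0.500 = 0.267. The Wilson limits are 0.591 to 0.882 for 23/30 and 0.332 to 0.668 for 15/30. The Newcombe limits are
- lower: 0.267 − √[(0.767 − 0.591)² + (0.668 − 0.500)²] = 0.023
- upper: 0.267 + √[(0.882 − 0.767)² + (0.500 − 0.332)²] = 0.471

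The interval excludes zero, in line with Boschloo's p-value and against Fisher's.

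**Step 5: covariate adjustment.** A standardised risk difference from a logistic model with four covariates was simulated in 36 scenarios (30, 40 and 50 per arm; covariate log-odds of 0, 0.2 and 0.4 per SD). Its interval was 0.97 to 1.08 times as wide as the unadjusted Newcombe interval, its coverage was 93.2% to 95.0%, and it disagreed with the Boschloo p-value in 1.9% to 14.4% of trials. No gain in precision was shown.

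**The case against.** The strongest objection is that nothing here is wrong. A pre-specified, valid exact test for secondary binary outcomes is a defensible and familiar choice, and preferring another test may be a matter of taste. It stands that this is not an error. But the preference rests on more than taste: Boschloo's test is never less powerful and respects the same limit. The same cannot be said of the mid-p or Pearson tests, whose maximum size at 30, 40 and 50 per arm is 5.2% to 5.9%.

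The second objection is to the size of the gain, and it stands. The larger figures need exactly equal arms. Because missing data are not imputed, the analysed arms may well differ by a patient or more, which roughly halves the median gain. A reader who looks only at arms of 30, 40 and 50 might infer that Fisher's size is always 3.5% or less, or that 5 to 7 points are routinely lost. Of the 231 pairs of arm sizes, 211 have a maximum size above 3.55%.

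A reader might also infer that leaving these outcomes unadjusted contradicts the plan. It does not: the SAP applies the adjusted approach only to the outcomes it lists, and these three are not among them. Nor can it be held against the SAP that it names no effect estimate or time points for them, since the protocol, which is not at hand, may do so.

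**Conclusion.** The point holds as a low-priority improvement. Fisher's test is valid here but uses only part of the 5%: at most about 2.7% to 3.8% with equal arms of 30 to 50, and up to about 4.8% with unequal arms. Replacing it with Boschloo's test gains a median of about 5 to 7 points of power with exactly equal arms, and about 2 to 4 with slightly unequal arms, where Fisher's power is 40% to 80%. It gains close to nothing where power is already high. That the gain is never negative does not depend on the assumptions; its size does, since level, arm sizes and response rates are all assumed.

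The stronger readings, that the planned test is wrong or that covariate adjustment is needed for these outcomes, are not supported by the SAP or by the calculations.

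**What to change.** Replace the sentence on Fisher's tests, leaving the dichotomies as they are, with:

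> For return to desired sport, patient satisfaction and PASS, dichotomised as stated, the two-sided p-value is taken from Boschloo's unconditional exact test, reported with the risk difference and its Newcombe 95% CI.

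An estimate adjusted for age, sex, BMI and duration of symptoms may be added as an optional, supplementary analysis. If the treatment code is already broken, keep Fisher's test as planned and label Boschloo's test as supplementary, so that the test is not chosen with the results in view.

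The cost is one sentence in the SAP. The downsides are software that is less familiar to many readers, a gain that can be close to zero, and occasional disagreement between the interval and the p-value near 5%. How often that happens with the Newcombe interval was not simulated; the 1.9% to 14.4% above is for the adjusted interval, which disagreed with Fisher's p-value in 2.5% to 19.6% of trials.
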